3. ANALYSIS SET

- Full Analysis Set
 The subjects who were randomized and given at least one dose of the study drug.
- Safety Analysis Set
 The subjects who are given at least one dose of the study drug.

4. CONSIDERATIONS for ANALYSIS

· Confidence coefficient

95% (two-sided estimation)

Display digit

[Mean, Confidence coefficient, Quartiles]

Round statistics down to the 1 digits lower than significant digits of the data.

[Standard Deviation]

Round statistics down to the 2 digits lower than significant digits of the data.

[Minimum and Maximum Values]

Display the data at the significant digits.

[Proportion, Percentage]

Round statistics off to 1 decimal places.

5. OTHER DATA HANDLING

[Definition of Daytime]

· Time zone from wake-up time to bedtime

[Definition of Nocturnal Period]

• Time zone from bedtime to wake-up time

[Data Handling for Study Drug]

· Duration of Treatment

Duration of Treatment = Date of the Last Dose – Date of the First Dose + 1

[Data Handling for Adverse Event]

- An adverse event is defined as any untoward medical occurrence in a patient or a subject receiving a pharmaceutical product (including the study drug). It does not necessarily have an apparent causal relationship with this pharmaceutical product (including study drug).
- Adverse events, excluding serious adverse events (protocol 10.1.3), shall be non-serious adverse events in the case of an incidence of over 5% in at least one treatment group.

[Data Handling for Laboratory Test Results]

Inhibitory Rate of DPP-4 Activity (%)
 Inhibitory rate of DPP-4 activity (%) = (DPP-4 activity at start of observation period –
 DPP-4 activity at each visit of treatment period) / DPP-4 activity at start of observation period x 100

[Data Handling for Duration of Diabetes (year)]

Duration of Diabetes (year)

Duration of diabetes (year) = (Date of Informed Consent (year/month) – Onset Date of

Diabetes (year/month)) / 12 (rounded off two decimal places)

If only the month of the onset of diabetes is unknown, the month of the onset of diabetes is regarded as "January".

6. SUBJECTS, DEMOGRAPHIC and OTHER BASELINE CHARACTERISTICS

- 6.1. Subject Disposition
- 6.1.1. Study Information

Analysis Set: All subjects who were obtained informed consent

Analysis Variables: The earliest date of informed consent

The latest date of the last date of administration

Version of MedDRA

Version of SAS

Analysis Methods: For the above analysis items, the following analysis is performed.

(1) Show above items.

6.1.2. Eligibility of Subjects

Analysis Set: All subjects who were obtained informed consent

Analysis Variables: Randomization into the treatment period of the study

[Yes, No (and the reason)]

Analysis Methods: For the above analysis items, the following analysis is performed.

(1) Frequency distribution

6.1.3. Exit Status of Subjects

Analysis Set: Randomized subjects

Analysis Variables: Exit status from the study

[Complete, Incomplete (and the reason)]

Analysis Methods: For the above analysis items, the following analysis is performed for each treatment group and all subjects in the analysis set.

(1) Frequency distribution

6.1.4. Protocol Deviations and Analysis Datasets

6.1.4.1. **Protocol Deviations**

Analysis Set: Randomized subjects

Analysis Variables: Protocol Deviations

[Major GCP Violations, Deviations of Protocol Entry Criteria, Deviations of Discontinuation Criteria, Deviations Related to Treatment Procedure or Dose, Deviations Concerning Excluded Medication or Therapy, Deviations to Avoid Emergency Risk, Other Deviations]

Analysis Methods: For the above analysis items, the following analysis is performed for each treatment group and all subjects in the analysis set.

(1) Frequency distribution

Summarize the number of subjects who have deviated from the protocol, classify the deviations into above category, and show the breakdown of deviations. Subjects applicable for multiple categories will be counted once in each category.

6.1.4.2. Datasets Analyzed

Analysis Set: Randomized subjects

Analysis Variables: Subjects excluded from analysis datasets [Reason of exclusion]

Full Analysis Set [Adopted] Safety Analysis Set [Adopted]

Analysis Methods: For the above analysis items, the following analysis is performed for each treatment group (both (1) and (2)) and all subjects (for (2)) in the analysis set. For analysis (1), Subjects applicable for multiple categories will be counted once in each category.

- (1) Frequency distribution in each analysis set about handling for subjects
- (2) Frequency distribution in each analysis set of adopted subjects.

6.2. Demographics and Other Baseline Characteristics

6.2.1. Distribution of Demographics Items

Analysis Set: Full Analysis Set

Analysis Variables:

Sex [Male, Female]

Height (Start of the observation period) (cm)

$$160 \le -170, 170 \le -180$$

Weight (Start of the observation period) (kg)

$$Min \le - <50.0, 50.0 \le - <60.0,$$

$$60.0 \le -80.0$$
, $70.0 \le -80.0$,

$$80.0 \le - \le Max$$

BMI (Start of the observation period) (kg/m²)

$$25.0 \le - \le Max$$

Smoking Classification [Never Smoked, Current Smoker, Ex-Smoker]

Drink Alcohol Almost Every Day? [Yes, No]

Duration of Diabetes Mellitus (Years) [Min<= - <5, 5<= - <10,

$$10 \le - \le Max$$

HbA1c (NGSP) (Start of the observation period) (%)

$$[Min \le - <7, 7 \le - <8, 8 \le - <=Max]$$

AUC over time when blood glucose 110 mg/dL is observed during the 3

hour time period after breakfast (Start of the observation period)

AUC over time when blood glucose 140 mg/dL is observed during the 3

hour time period after breakfast (Start of the observation period)

AUC over time when blood glucose 160 mg/dL is observed during the 3 hour time period after breakfast (Start of the observation period)

AUC over time when blood glucose 180 mg/dL is observed during the 3

hour time period after breakfast (Start of the observation period)

AUC over time when blood glucose 110 mg/dL is observed during the 3

hour time period after lunch (Start of the observation period)

AUC over time when blood glucose 140 mg/dL is observed during the 3

hour time period after lunch (Start of the observation period)

AUC over time when blood glucose 160 mg/dL is observed during the 3

hour time period after lunch (Start of the observation period)

AUC over time when blood glucose 180 mg/dL is observed during the 3

hour time period after lunch (Start of the observation period)

AUC over time when blood glucose 110 mg/dL is observed during the 3 hour time period after evening meal (Start of the observation period)

AUC over time when blood glucose 140 mg/dL is observed during the 3 hour time period after evening meal (Start of the observation period)

AUC over time when blood glucose 160 mg/dL is observed during the 3 hour time period after evening meal (Start of the observation period)

AUC over time when blood glucose 180 mg/dL is observed during the 3 hour time period after evening meal (Start of the observation period)

AUC over time during periods when blood glucose 140 mg/dL is observed (start of the observation period)

AUC over time during periods when blood glucose 160 mg/dL is observed (Start of the observation period)

AUC over time during periods when blood glucose 180 mg/dL is observed (Start of the observation period)

Cumulative time during periods when blood glucose 140 mg/dL is observed (Start of the observation period)

Cumulative time during periods when blood glucose 160 mg/dL is observed (Start of the observation period)

Cumulative time during periods when blood glucose 180 mg/dL is observed (Start of the observation period)

AUC over time during periods when blood glucose <70 mg/dL is observed (Start of the observation period)

Peak postprandial glucose over time 3 hours after breakfast (Start of the observation period)

Peak postprandial glucose over time 3 hours after lunch (Start of the observation period)

Peak postprandial glucose over time 3 hours after evening meal (Start of the observation period)

Maximum variation of blood glucose over time between before and after breakfast (Start of the observation period)

Maximum variation of blood glucose over time between before and after lunch (Start of the observation period)

Maximum variation of blood glucose over time between before and after evening meal (Start of the observation period)

MAGE (Start of the observation period)

Mean 24-hour blood glucose (Start of the observation period)

Mean daytime blood glucose (Start of the observation period)

Mean nocturnal blood glucose (Start of the observation period)

AUC (Start of the observation period)

AUC over time during periods when blood glucose 110 mg/dL is observed (Start of the observation period)

SD of 24-hour blood glucose (Start of the observation period)

SD of daytime blood glucose (Start of the observation period)

SD of nocturnal blood glucose (Start of the observation period)

Glycoalbumin (Start of the observation period)

1,5-AG (Start of the observation period) [Min<= - <10,
$$10$$
<= - <14, 14 <= - <=Max]

Fasting blood glucose (Start of the observation period)

Fasting insulin (Start of the observation period)

Fasting glucagon (Start of the observation period)

Fasting proinsulin (Start of the observation period)

Fasting GLP-1 (Start of the observation period)

Fasting GIP (Start of the observation period)

DPP-4 Activity (Start of the observation period)

Analysis Methods: For the above analysis items, the following analysis is performed for each treatment group and all subjects in the analysis set.

(1) Frequency distribution for discrete variables and summary statistics for continuous variables

6.2.2. Medical History and Concurrent Disease

Analysis Set: Safety Analysis Set

Analysis Variables: Medical history, Concurrent disease

Analysis Methods: For the above analysis items, the following analysis is performed for each treatment group. Analysis variables will be coded using the MedDRA dictionary and be summarized into SOC and PT. SOCs will be sorted in alphabetical order, then PTs will be sorted in frequency order.

- (1) Frequency of medical history by SOC/PT
- (2) Frequency of concurrent disease by SOC/PT

The method of accounting for the frequency is as follows.

[Number of subjects with AE]

Within each summary, subjects with one or more events within a level of SOC term is counted only once in that level. Similarly, subjects with one or more events within a level of PT term is counted only once in that level.

6.2.3. Prior and Concomitant Medication

Analysis Set: Safety Analysis Set Analysis Variables: Prior medication

Concomitant medication

Analysis Methods: For the above analysis items, the following analysis is performed for each treatment group. Analysis variables will be coded using the WHO (World Health Organization) Drug. Coded medications will be sorted in frequency order. Medications used more than once within a subject will be counted only once for the subject.

- (1) Frequency of prior medication
- (2) Frequency of concomitant medication

6.3. Treatment Compliance

6.3.1. Study Medication Compliance

Analysis Set: Safety Analysis Set

Analysis Variables: Study medication compliance

[Fully Complied (75% or More),

Not Compliant (Less than 75%)]

Time Point: Visit 5 or time of discontinuation

Analysis Methods: For the above analysis items, the following analysis is performed for each treatment group and all subjects in the analysis set by time point.

(1) Frequency

6.3.2. Diet Therapy Compliance

Analysis Set: Safety Analysis Set

Analysis Variables: Diet therapy [Yes, No]

Diet therapy compliance [Fully complied (90% or More), Almost complied (70% or more),

Occasionally complied (50% or more),

Rarely complied (Less than 50%)]

Time Point: Visit3, Visit4, Visit 5 or time of discontinuation

Analysis Methods: For the above analysis items, the following analysis is performed for each treatment group and all subjects in the analysis set by time point.

(1) Frequency

6.3.3. Exercise Therapy Compliance

Analysis Set: Safety Analysis Set

Analysis Variables: Exercise therapy [Yes, No]

Exercise therapy compliance

[Fully complied (90% or more),

Almost complied (70% or more),

Occasionally complied (50% or more),

Rarely complied (Less than 50%)]

Time Point: Visit3, Visit4, Visit 5 or time of discontinuation

Analysis Methods: For the above analysis items, the following analysis is performed for each treatment group and all subjects in the analysis set by time point.

(1) Frequency

6.3.4. Study Medication Exposure

Analysis Set: Safety Analysis Set

Analysis Variables: Duration of exposure (days)

Analysis Methods: For the above analysis items, the following analysis is performed for each treatment group and all subjects in the analysis set.

(1) Summary statistics of continuous variables

7. EFFICACY EVALUATIONS

7.1. Primary Endpoint and the Analytical Methods

Analysis Set: Full Analysis Set

Analysis Variables: Changes in the standard deviation (SD) of 24-hour blood glucose values

Time Point: Start of the observation period, CGM in treatment period (Day 2, Day 3,

Day 4, Day 5, Day 6, Day 7, Day 8)

Covariate: HbA1c (NGSP) at start of the observation period (%)

[Continuous variable]

SD of 24-hour blood glucose at start of the observation period

[Continuous variable]

Age (years old)

 $[<65,65 \le Max]$

Analysis Methods: For the above analysis items, the following analysis is performed.

- (1) Summary statistics and two-sided 95% confidence interval (CI) by time point (each Day) will be calculated by treatment group. The time course will be presented graphically using the mean change and SD. Then, point estimates of the difference of mean between treatment groups (Trelagliptin 100 mg group Alogliptin 25 mg group) and its two-sided 95% CI will be calculated.
- (2) To estimate adjusted mean and two-sided 95% CI of each treatment group, adjusted difference of mean between treatment groups (Trelagliptin 100 mg group Alogliptin 25 mg group) and its two-sided 95% CI, analysis of covariance (ANCOVA) will be performed by time point using change from start of the observation period of SD of 24-hour blood glucose as a dependent variable, treatment group as an independent variable, HbA1c (NGSP) and SD of 24-hour blood glucose at start of the observation period and age as covariates.

7.2. Secondary Endpoints and the Analytical Methods

Analysis Set: Full Analysis Set

Analysis Variables:

AUC over time when blood glucose 110 mg/dL is observed during the 3 hour time period after breakfast

AUC over time when blood glucose 140 mg/dL is observed during the 3 hour time period after breakfast

AUC over time when blood glucose 160 mg/dL is observed during the 3 hour time period after breakfast

AUC over time when blood glucose 180 mg/dL is observed during the 3 hour time period after breakfast

AUC over time when blood glucose 110 mg/dL is observed during the 3

hour time period after lunch

AUC over time when blood glucose 140 mg/dL is observed during the 3 hour time period after lunch

AUC over time when blood glucose 160 mg/dL is observed during the 3 hour time period after lunch

AUC over time when blood glucose 180 mg/dL is observed during the 3 hour time period after lunch

AUC over time when blood glucose 110 mg/dL is observed during the 3 hour time period after evening meal

AUC over time when blood glucose 140 mg/dL is observed during the 3 hour time period after evening meal

AUC over time when blood glucose 160 mg/dL is observed during the 3 hour time period after evening meal

AUC over time when blood glucose 180 mg/dL is observed during the 3 hour time period after evening meal

AUC over time during periods when blood glucose 140 mg/dL is observed

AUC over time during periods when blood glucose 160 mg/dL is observed

AUC over time during periods when blood glucose 180 mg/dL is observed

Cumulative time during periods when blood glucose $140\ mg/dL$ is observed

Cumulative time during periods when blood glucose 160~mg/dL is observed

Cumulative time during periods when blood glucose 180 mg/dL is observed

AUC over time during periods when blood glucose <70 mg/dL is observed

Peak postprandial glucose over time 3 hours after breakfast

Peak postprandial glucose over time 3 hours after lunch

Peak postprandial glucose over time 3 hours after evening meal

Maximum variation of blood glucose over time between before and after breakfast

Maximum variation of blood glucose over time between before and after lunch

Maximum variation of blood glucose over time between before and after evening meal

MAGE

Mean 24-hour blood glucose

Mean daytime blood glucose

Mean nocturnal blood glucose

AUC

AUC over time during periods when blood glucose 110 mg/dL is observed

SD of 24-hour blood glucose

SD of daytime blood glucose

SD of nocturnal blood glucose

Time Point: Start of the observation period, CGM in treatment period (Day 2, Day 3,

Day 4, Day 5, Day 6, Day 7, Day 8)

Covariate: HbA1c (NGSP) at start of the observation period (%)

[Continuous variable]

SD of 24-hour blood glucose at start of the observation period

[Continuous variable]

Age (years old)

 $[< 65, 65 \le Max]$

Analysis Methods: For the above analysis items, the following analysis is performed

- (1) The same analyses described in 7.1(1) and (2) will be performed on measurement values and changes from start of the observation period at each time point. For the SD of 24-hour blood glucose, only the measured value will be shown.
- (2) The same analyses described in 7.1(1) and (2) will be performed on means of 7days and changes from start of the observation period during Week 3-4 at treatment period. The time course will be presented graphically using only means and SDs of each treatment group.

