13.1.3 Efficacy analysis

[Primary endpoints]

Changes in the SD of 24-hour blood glucose values (mg/dL) for each 7-day period between
 Week 3 and Week 4 (between Day 22 and Day 28) of the treatment period, calculated from the value at the start of the observation period

(Analysis method)

- ·For the "full analysis set", summary statistics (number of subjects, mean, SDs, maximum values, minimum values, quartiles [same apply hereafter]) and 95% confidence interval (two sides) of mean shall be calculated for each treatment group at each evaluation point (each day), and illustrating changes in mean and SD in order to evaluate changes in the SD of 24-hour blood glucose values (mg/dL) for each 7-day period between Week 3 and Week 4 (between Day 22 and Day 28) of the treatment period, calculated from the value at the start of the observation period for trelagliptin or alogliptin separately.
- · Preliminary, for the "full analysis set", calculate point estimation and 95% confidence interval (two

sides) in difference of mean in treatment groups (trelagliptin 100 mg group – alogliptin 25 mg group) in order to examine the influence of the once-weekly administration and blood glucose fluctuations due to the difference in the daily administration exploratory.

- · As well, for the "full analysis set," conduct analysis of covariance at each evaluation point with changes in the SD of 24-hour blood glucose values between Week 3 and Week 4 from the value at the start of the observation period as dependent variable, treatment groups as independent variable, HbA1c (NGSP value) at the start of the observation period, changes in the SD of 24-hour blood glucose values at the start of the observation period, and age as covariates, and calculate point estimation and 95% confidence interval (two sides) in difference of adjusted mean for each group.
- · Preliminary, "full analysis set," calculate point estimation and 95% confidence interval (two sides) in difference of adjusted mean in treatment groups (trelagliptin 100 mg group alogliptin 25 mg group)

[Secondary endpoints]

- Changes in AUC over time when specific blood glucose levels (110, 140, 160, or 180 mg/dL) are observed during the 3 hour time period after breakfast, lunch and evening meal*1, 2
- Change in AUC over time during periods when blood glucose 140, 160, or 180 mg/dL (hyperglycemia) is observed*1,2
- Changes in blood glucose 140, 160, or 180 mg/dL (hyperglycemia) over time*1,2

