- Changes in AUC over time during periods when blood glucose < 70 mg/dL (hypoglycemia) is observed*1,2
- Change in peak postprandial glucose levels over time 3 hours after breakfast, lunch, and evening meal*1,2
- Change in maximum variation of blood glucose levels over time between before and after breakfast, lunch, and evening meal *1, 2
- Changes in MAGE*1, 2
- Changes in mean 24-hour blood glucose levels *1, 2
- Changes in mean daytime blood glucose levels*1,2
- Changes in mean nocturnal blood glucose levels*1, 2
- Changes in AUC*1, 2
- Changes in AUC over time during periods when blood glucose 110 mg/dL is observed*1,2
- Changes in the SD of 24-hour blood glucose values*1,2
- Changes in the SD of mean daytime blood glucose values*1,2
- Changes in the SD of mean nocturnal blood glucose values*1,2
 - *1: Measured value and percent changes for the each 7-day period between Week 3 and Week 4 (between Day 22 and Day 28) of the treatment period calculated from the value at the start of

the observation period (however changes in the SD of 24-hour blood glucose values shall be measured value only)

*2: Percent change from the value at the start of the observation period to the mean value during the 7-day period between Week 3 and Week 4 (between Day 22 and Day 28) of the treatment period

(Analysis method)

• Conduct the same analysis as the primary endpoints for *1 and *2 of the above endpoint section. However, for changes in mean/SD, only measured values of *1 and *2 shall be illustrated.

[Other endpoints]

- Glycoalbumin
- 1,5-AG
- Fasting blood glucose
- Fasting insulin
- Fasting glucagon
- Fasting proinsulin
- FastingGLP-1
- Fasting GIP
- DPP-4 activity
- Inhibitory rate of DPP-4 activity

(Analysis method)

Calculate summary statistics and 95% confidence interval (two sides) of mean at each
evaluation point (the start of the observation period by each treatment group, first day, 1 point
during third to fifth day, and ninth day of CGM which is to be performed for 9 days from Day
21) in measured values and changes from the start of the observation period, and illustrate
changes in mean and SD

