SD of nocturnal blood glucose

Time Point: Start of the observation period, CGM in treatment period (Day 2, Day 3,

Day 4, Day 5, Day 6, Day 7, Day 8)

Covariate: HbA1c at start of the observation period (NGSP) (%)

[Continuous variable]

SD of 24-hour blood glucose at start of the observation period

[Continuous variable]

Age (years old)

[Continuous variable]

Analysis Methods: For the above analysis items, the following analysis is performed

(1) Correlation coefficients between secondary endpoints and covariates will be calculated by time Point.

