10.1. Adjustments for Covariates

ANCOVA will be performed on primary and secondary endpoints using treatment group as independent variables, HbA1c (NGSP) at the start of the observation period and SD of 24-hour blood glucose at the start of observation period as covariate. Details are described in 7.1, 7.2 and 7.3.4.

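### SAP 7.2 and 10.1 adjust 33 of the 34 secondary CGM variables for baseline 24-hour SD but not for their own baseline, so part of the chance imbalance remains and the measured-value and absolute-change results can disagree

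*SAP*

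**What the plan says.** SAP 7.1 models change in the SD of 24-hour glucose with treatment, HbA1c, baseline 24-hour SD and age group. There, baseline 24-hour SD is the endpoint's own baseline.

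SAP 7.2 lists the same three covariates, including "SD of 24-hour blood glucose at start of the observation period", for every secondary variable. It then states: "The same analyses described in 7.1(1) and (2) will be performed on measurement values and changes from start of the observation period". This is done at each time point and again for the 7-day mean. SAP 10.1 covers primary and secondary endpoints together, with HbA1c and "SD of 24-hour blood glucose at the start of observation period as covariate", and refers to 7.1, 7.2 and 7.3.4 for detail. Neither section adds an endpoint-specific baseline.

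The own baselines are available. SAP 6.2.1 tabulates the secondary CGM variables at the start of observation, for example "Mean 24-hour blood glucose (Start of the observation period".

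Protocol 13.1.3 names the primary covariates as HbA1c, "changes in the SD of 24-hour blood glucose values at the start of the observation period, and age as covariates". For the secondary endpoints it says: "Conduct the same analysis as the primary endpoints for *1 and *2 of the above endpoint section".

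**The concern.** Baseline 24-hour SD is the natural adjuster for the primary endpoint. It is a weaker one for mean glucose, postprandial peaks or time above a threshold. Randomisation is stratified only by HbA1c and age, so the other CGM baselines are balanced by chance alone, at 15 per arm.

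Two things are at stake for the between-arm secondary estimates. First, the part of a chance baseline difference that HbA1c and 24-hour SD do not capture is carried into the adjusted difference. It pushes the measured-value result one way and the change result the other. Second, one endpoint gets two adjusted treatment differences, and the SAP does not say which to read.

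**Working it through.** **Count, from the SAP 7.2 list.** 12 postprandial AUCs (4 thresholds × 3 meals) + 3 AUCs (140, 160, 180 mg/dL) + 3 cumulative times + 1 AUC <70 + 3 peaks + 3 before/after-meal maxima + 1 MAGE + 3 means + 1 total AUC + 1 AUC at 110 + 3 SDs = 34. Only SD of 24-hour glucose has its own baseline in the model, so 34 − 1 = 33 do not. By type these are 4 levels, 20 threshold AUCs or times, 3 peaks and 6 variability measures.

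**Identity.** Let Y be the follow-up value, B the own baseline, and X the SAP design matrix (treatment, HbA1c, baseline 24-hour SD, age group). Least squares is linear in the outcome, so on the same subjects

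effect(Y) − effect(Y − B) = effect(B),

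which is the X-adjusted baseline difference between arms. If B is a column of X, effect(B) = 0 and the two results coincide. This needs no assumption about the data. It holds for absolute change only. The unadjusted differences in SAP 7.1(1) ("Then, point estimates of the difference of mean between treatment groups") keep the raw baseline difference as their gap whatever the covariates.

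B is the same for all seven days and for the 7-day mean. There are therefore 33 distinct gaps, each repeated eight times when the same subjects are analysed.

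**Size of the gap.** Inputs: 15 per arm (Protocol 13.3), and q, the share of own-baseline variance explained by HbA1c and 24-hour SD. The documents do not give q, so it is assumed. SE = √(1 − q) × √(2/15), in baseline SD units.

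| q | Formula | Simulated SD of gap |
|---|---|---|
| 0 | 0.365 | 0.38–0.39 |
| 30% | 0.306 | 0.32–0.33 |
| 50% | 0.258 | 0.27–0.28 |
| 90% | 0.115 | 0.12 |

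With B added, the simulated gap was below 1e-13.

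**Imbalance left in.** In a simulation with no true effect (correlation of own baseline with follow-up 0.5–0.8, with baseline 24-hour SD 0–0.9), each 1 SD of raw baseline imbalance moved the measured-value estimate by +0.10 to +0.66 SD and the change estimate by −0.04 to −0.42 SD. With B added, both slopes were about 0.

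**Confidence-interval width, SAP model plus B relative to SAP model.** Residual df go from 30 − 5 = 25 to 24. The simulation had 24 cells of 6,000 trials: baseline-to-follow-up correlation 0.3, 0.5 or 0.7; the four q values; and partial correlation of follow-up with 24-hour SD, given B, of 0 or 0.3.

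| Assumption | Measured value | Absolute change |
|---|---|---|
| q 0–50%, partial 0 | 0.730–0.999 | 0.826–0.980 |
| q 0–50%, partial 0.3 | 0.713–1.023 | 0.792–0.935 |
| q 90%, partial 0 | 0.979–1.017 | 0.995–1.013 |
| q 90%, partial 0.3 | 1.005–1.023 | 0.900–0.938 |

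The best cells are 1 − 0.730 = 27% and 1 − 0.713 = 29% narrower. The worst is 2.3% wider. Coverage of the SAP model was 94.6–95.7%.

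**One worked case.** Take correlations B with 24-hour SD 0.7, Y with B 0.4, and Y with 24-hour SD 0.5. Residual variance for measured value is 1 − 0.5² = 0.75 under the SAP model. For change it is 1.2 − 0.2² = 1.16. With both covariates each is 0.745. In simulation, adding B made the measured-value interval 2% wider and the change interval 18% narrower. The two SAP-model estimates had opposite signs in 23%, 17% and 9% of trials at true differences of 0, 0.3 and 0.5 SD.

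**The case against.** The strongest reply is that the plan already shows the discrepancy. SAP 7.2 lists the start of observation as a time point and runs the ANCOVA on measured values at each one. Read literally, that outputs the adjusted baseline difference, and a reader could reconcile the two answers by subtraction. This stands, and it limits the harm. It does not recover the lost precision or say which answer to read.

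The SAP also follows a fair reading of the protocol. "Conduct the same analysis as the primary endpoints for *1 and *2 of the above endpoint section" can mean the literal covariate list, or adjustment for the endpoint's own baseline as in the primary model. A reader might infer that the SAP departs from the protocol. The text does not support that.

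The study is exploratory. Its between-arm comparison is secondary and preliminary, results are estimates with 95% intervals, and sample size was set on feasibility. That stands and sets the severity. Opposite signs at zero true difference partly reflect estimates scattering around zero.

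Three stronger readings are tempting:

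- **Bias.** A reader might infer that the secondary estimates are biased. Under randomisation they are not, and HbA1c and 24-hour SD already remove part of the imbalance. For the six variability measures that part may be most of it.
- **Hundreds of conflicts.** Multiplying 33 variables by eight analyses gives 264 pairs, but with the same subjects these repeat 33 gaps.
- **SAP 7.3.4.** It also omits baseline mean glucose. However, it models change only, so the two-answer problem cannot arise. It estimates background-factor coefficients, HbA1c among them, and an added baseline would change what these mean. No calculation here supports extending the point to it.

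Finally, all sizes rest on assumed correlations, and no simulated cell has zero-heavy data, as some of the 20 threshold variables may. SAP 7.3.2 ("Correlation coefficients between secondary endpoints and covariates will be calculated by time Point") will show how baselines track 24-hour SD, but not how each tracks its own follow-up.

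**Conclusion.** The point holds as a minor inefficiency and ambiguity. The count of 33 and the identity follow from the SAP text and from algebra. The gap's standard error of about 0.12 to 0.37 baseline SD, and the width changes from about 2% wider to 27–29% narrower, depend on the assumed correlations. The benefit is likely smallest for variables close to 24-hour SD and larger for levels, peaks and threshold measures that track it less. If the changes in SAP 7.2 are meant as the percent change in Protocol 13.1.3, the measured-value and change results can still differ after the fix. Only the gain from own-baseline adjustment would then remain.

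**What to change.** In SAP 7.2 and 10.1, for the secondary endpoints at Day 2 to Day 8 and for the 7-day mean, **add** to HbA1c, baseline 24-hour SD and age group: *the start-of-observation value of the endpoint analysed [continuous variable]*.

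- Leave the start-of-observation time point on the current covariates. There the added covariate would equal the outcome.
- Leave SD of 24-hour glucose unchanged, since its own baseline is already included.
- The current covariates may be kept for AUC <70 mg/dL and for any other threshold variable whose baseline is mostly zero. Name those variables in the SAP. Their gap remains.
- State that the measured-value and absolute-change models otherwise give the same adjusted difference, and that percent-change and unadjusted differences can still differ.
- Record the addition in the revision history.

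Add rather than replace: substituting the own baseline for 24-hour SD could widen the measured-value interval by up to 5–6% under the same kind of assumptions, and would drop a covariate that Protocol 13.1.3 names.

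The cost is a few lines of text, one more term in the analysis program, one residual degree of freedom (25 to 24) and an interval up to about 2% wider where 24-hour SD already captures the own baseline. No new data are needed.
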